expectation that younger populations of women and adolescent females will prefer and be more apt to utilize the CASI administration. As such, assessment of the BHI in both modes is critical to assess the validity by mode of administration as well as to evaluate survey completion rates based on demographic characteristics. These data will optimize recruitment and survey administration methods for future population based cohort studies.

Some scales have shown that while there are mode effects, the underlying psychometric properties of multi-dimensional scales can remain constant between modes.^{8,9} Other potential biases or sources of error associated with mode of administration are unknown. While a computer mode may increase efficiency of questionnaire completion, it also may produce measurement error; use of a computer may alter the distribution of BHI scores.^{8,9} However, where any change in distribution is found to be constant, this effect can be controlled by score calibration. Therefore, a mode experiment to identify and/or quantify any effect of mode of administration is included in the study protocol.

III. PRELIMINARY DATA

The process of developing and validating a measurement instrument is iterative. Generally, the sequence of tasks for the BHI development is:

1. Development of conceptual model with well specified constructs (or dimensions)
2. Generation of an item pool of new or existing items mapped to constructs
3. Cognitive evaluation of items (face/content validity)
4. Reliability and validity analyses
5. Responsiveness, evaluation of sensitivity to change
6. Establishment of validity in special populations (Spanish fluent and adolescents)

Figure 2 (below) depicts the consortium’s overall plan for development and validation of a bladder health measurement scale (BHS). Steps 1 and 2 have been completed. Step 3 is expected to be completed by May 2019. Step 4, the proposed validation work of this protocol, will commence by June 2019 and be complete by spring 2020. Steps 5 and 6 are planned to be completed through future protocols.

[figure not shown]

Figure 2. Schematic of the overall plan for a bladder health instrument development and validation

III.A. Conceptual framework and item pool

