- Able to read and provide informed consent

Exclusion criteria:

- Physical or mental condition that would prohibit self-administration of questionnaire either electronically or using paper and pencil (e.g. dementia/cognitive impairment/blindness/severe arthritis).
- Institutional living arrangement e.g. skilled nursing, long term care or rehabilitation center (these are not included in DSF)

The sampling and recruitment flow for the general population sample is shown in Figure 4. Following random assignment (RA) to PAPI or CASI mode, all households will be mailed a pre-notice letter including a tri-fold color brochure describing the study. The pre-notification mailing will include a \$2.00 bill. Households randomized to CASI will also be asked to provide a valid email address using the provided postage paid return envelope. The return rate due to a bad address of 3% is expected. Upon notification of a return due to a bad address, the address will be removed from the sample.

IV.B.2.a. PAPI mode

One week following mailing of prenotification letter, households randomly assigned to a PAPI survey version will be mailed a validation version survey packet (BHI, criterion questions and demographics) with a request for the survey to be completed by the female age 18 or over with the most recent birthday. This mailing will include \$10 as incentive and a stamped envelope addressed to the SDCC. Twenty two days later, households that do not respond to the initial validation survey will be mailed a 2nd validation survey packet. Twenty two days following the 2nd mailing, non-respondent households will be mailed a third validation survey, and 22 days following this mailing the 4th and final validation survey packet will be sent to non-respondent households, for a total of 5 contact points. It is reasonable to expect response rates to survey

mailings of 10%, 7%, 5% and 3% for each successively mailed survey, respectively, thus the number of households sampled is estimated to be 1500 in order to achieve 333 responses.

IV.B.2.b. CASI mode

Households randomly assigned to the CASI mode will be asked to provide an email address. Respondents who do not provide an email will be assigned to the “push to web” group. The push to web group will be mailed a letter that includes a URL for survey completion.

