Households randomly assigned to the CASI mode who do provide an email address will be further randomized to the push to web group or to receive an email with a link to the survey (referred to as the direct email group). This second randomization will allow a full comparison of respondents who fully elect to respond via electronic mode to those who do not. A total of four follow-up letters with a URL to an electronic version of the survey packet will be mailed to non-respondent households of this push-to-web group at 16 day intervals, and between the 2nd and 3rd letter sent, non-respondents will be mailed a paper version of the survey, for a total of 6 contact points. Respondents who provide an email address and who are randomized to the direct email group will be sent an email that contains a URL link to an electronic version of the survey packet. A total of four follow-up emails with a URL link to an electronic version of the survey packet will be emailed to non-respondents at one-week intervals, also with a paper version of the survey mailed between the 2nd URL and 3rd URL, for a total of 6 contact points.

Response rates are expected to differ from PAPI mode, with an expectation of a 10% overall response rate to the request for CASI completion.¹⁵ With the use of a listed DSF frame, households will be randomized to account for expected differential response rates between paper and electronic completion. Within budget allowances, households assigned to an electronic version that do not complete the survey electronically will then be sent a paper version of the survey.

IV.B.2.c. Data Sharing with NIDDK Repository

For both the PAPI and CASI groups, participants will be randomized 1:1 to the placement/timing of receiving text regarding data sharing with NIDDK repository. One group will receive the text immediately at the end of the BHI and the other group will receive the text separately after all study surveys are completed.

[figure not shown]

Figure 4a Stage 1 General Population Sample Plan

Stage 2
Retest and Bladder Diary

[figure not shown]

Figure 4b Stage 2 General Population Retest and Diary Sample Plan

IV.B.3. Retest and 2- day Bladder

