To the extent that a computer may increase respondent control or increase efficient use of completion time, this may produce some measurement error, but not threaten measurement validity. But if use of a computer (or a paper scale version) alters the distribution of BHI scores, or either mode is found to be a source of systematic variance in BHI score, validity may be threatened.⁷ Response to each individual items will be compared between PAPI and CASI for mode differences. Bland-Altman plots and analysis will be used to compare mean differences using limits of agreement for 95% confidence intervals of items across PAPI and CASI mode. Items that do not fall within LoA will be flagged as being a potential problem for psychometric evaluation. Additionally, psychometric evaluation of dimensions will be done independently for each mode and the final factor structures, including Cronbach alpha, the Kaiser-Guttman rule (Eigenvalues>1.0), factor loading thresholds of 0.60/.40, and scree plots, will be compared. If the structures are the same, then it is assumed that, while mode differences exist for some items, at the aggregate level the internal relationship between items for each factor are consistent. If the structures are not similar, the focus will be on determining if the items that demonstrate significant mode effects do in fact contribute to the structure difference, accomplished by evaluating the factor structures when these items are removed, using the same threshold criteria list above. The goal is to have a single instrument that is capable or working in either PAPI or CASI, recognizing the possibility that measurement differences between modes could result in sub-scales containing different items for each mode. A comparison of responses by mode: PAPI and CASI, will be made both between and within responses from the general population sample and the clinical sample and will also include comparison of item missing values.

IV.E.2.c. External Criterion Validity

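### General-population mode effects are read from respondents only, at an expected 22% response on paper against 10% to the web request, with no adjustment named, so who answered can be mistaken for how they answered

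*Protocol*

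**What the plan says.** **Assignment and contact (Protocol IV.B.1 and IV.B.2).** Sampled households are randomised to PAPI or CASI, then contacted.

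- Paper households get a pre-notice and up to four survey packets. The last packet "will be sent to non-respondent households, for a total of 5 contact points".
- Web households are asked for an email address, and then go to a push-to-web or a direct-email track. Each track has six contact points, one of which is a mailed paper survey.

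**Expected response.** For paper, IV.B.2.a assumes response to "mailings of 10%, 7%, 5% and 3% for each successively mailed survey, respectively", and "thus the number of households sampled is estimated to be 1500 in order to achieve 333 responses". For web, IV.B.2.b says "Response rates are expected to differ from PAPI mode, with an expectation of a 10% overall response rate to the request for CASI completion". It deals with the gap by setting how many households go to each mode. The targets in IV.E.3 are 333 paper and 361 web completes.

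**Who is expected to respond.** Section II, under Aim 4, gives as a reason for testing both modes the "expectation that younger populations of women and adolescent females will prefer and be more apt to utilize the CASI administration".

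**Analysis.** IV.E.2.b states: "Response to each individual items will be compared between PAPI and CASI for mode differences". Items outside Bland-Altman limits are flagged. Factor structures are fitted separately by mode and compared. If they differ, the mode-sensitive items are removed to see whether they account for it. No covariate, weight or non-response term is named.

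**Possible use.** Section II adds that "where any change in distribution is found to be constant, this effect can be controlled by score calibration".

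**The concern.** Randomising households makes the two sets of invited households comparable. It does not make the two sets of respondents comparable when most households do not answer and the chance of answering depends on the mode offered. The protocol predicts both conditions: response on paper about twice that to the web request, and an age gradient in willingness to use the web.

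Age defines the life-course strata in IV.E.3, so the protocol treats it as relevant to bladder health. If web respondents are younger, item distributions can differ between modes with no effect of the medium at all. Sound items could then be flagged as mode-sensitive, or a true mode effect could be cancelled by an opposite difference in respondents. Factor structure is exposed too. A shift in means alone leaves it unchanged, but a different mix of symptom levels need not, and IV.E.2.a itself plans to check whether the structure holds across LUTS severity.

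**Working it through.** **1. Reproduce the paper response.** Inputs from IV.B.2: 1500 households, successive response of 10%, 7%, 5% and 3%, and "The return rate due to a bad address of 3% is expected".

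- Deliverable addresses: 1500 × 0.97 = 1455.
- Cumulative response among those still outstanding: 1 − (0.90 × 0.93 × 0.95 × 0.97) = 0.2287.
- Responses: 1455 × 0.2287 = 332.8, matching the stated 333. As a share of households sampled, 333/1500 = 22.2%.
- Other readings do not match: 343.1 without the bad-address loss; 375 if the four rates are added (363.8 after bad addresses).

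**2. Web response.** At 10%, 361 completes need 361/0.10 = 3610 households, or 3610/0.97 = 3722 allowing for bad addresses. The ratio of expected response is 22.2/10 = 2.2. Sampling more web households equalises the number of completes, not their composition.

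**3. Precision of a mode difference.** SE = √(1/333 + 1/361) = 0.076 SD. The difference detectable with 80% power at two-sided 0.05 is (1.960 + 0.842) × 0.076 = 0.21 SD.

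**4. How large could selection be with no true mode effect?** The protocol gives no figure, so this is a range under assumptions. Let ρ be the correlation between the propensity to respond and the score. Under a latent-normal response model, respondents' mean is shifted by ρ × φ(z)/p SD, where p is the response rate and z its normal cut-off. The multiplier φ(z)/p is 1.341 at 22.2% and 1.755 at 10%.

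| Assumed ρ, paper / web | Apparent difference | In SEs |
|---|---|---|
| 0.1 / 0.1 | 0.1 × (1.755 − 1.341) = 0.04 SD | 0.5 |
| 0.3 / 0.3 | 0.3 × 0.414 = 0.12 SD | 1.6 |
| 0.5 / 0.5 | 0.5 × 0.414 = 0.21 SD | 2.7 |
| +0.1 / −0.1 | 0.1 × (1.341 + 1.755) = 0.31 SD | 4.1 |

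**5. The same through age mix, also assumed.** Spurious difference = gap in share of older women × age effect. A gap of 20 points with an effect of 0.5 SD gives 0.20 × 0.5 = 0.10 SD. A gap of 30 points with 0.8 SD, an extreme pairing, gives 0.30 × 0.8 = 0.24 SD.

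Selection that is weak and alike in both modes does little harm. Selection that differs by mode, which is what the stated age expectation implies, can match or exceed the detectable difference even when weak.

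**The case against.** **Silence is not a decision against adjustment.** IV.E.2.b does not say the comparison is unadjusted, and a separate SAP may add covariates. That stands as a caution. However, the protocol states the comparison, the flag and the consequences, and no step separates respondent mix from mode.

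**The protocol already attends to differential response.** It plans to examine completion rates by demographic group, randomises women who give an email between two web tracks, and compares modes in the clinical sample, where mode is block-randomised after enrolment (IV.C.2.a). These are real strengths. The first describes the problem, the second makes no contrast with paper, and the third concerns another sample that is not pooled. None corrects the general-population estimate. The clinical comparison also places women without email in PAPI, so it is clean only among those actually randomised.

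**Stronger readings that the text does not support:**

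- *That selection will be calibrated into the score.* A reader might infer this from Section II, but that passage says only that calibration can be used. IV.E.2.b contains no calibration step; its first consequence is a flag.
- *That unequal contacts favour paper.* The extra contact is in the web arm, which has the lower expected response.
- *That the incentive favours paper.* IV.B.2.a describes $10 enclosed with the paper packet, but IV.G lists $10 for the initial survey without restricting it to a mode, plus $5 for an email. Enclosure may differ; a difference in amount is not shown.
- *That 22% and 10% are total response for each arm.* The 10% refers to the request for web completion. Web non-respondents are also mailed paper, so total response in that arm may be higher. That adds crossover and does not remove selection.
- *That the SE and detectable difference give the chance of a false flag.* The flag uses limits of agreement, not a significance test.

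**Conclusion.** The concern holds in a limited form. The stated general-population comparison mixes the effect of the medium with differences in who responded, at an expected 22.2% on paper against 10% to the web request. Both rates, the age expectation and the absence of any named adjustment are in the protocol.

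The size of the bias is not known. The 0.04 to 0.31 SD range depends on assumed correlations and a normal response model, and the 0.10 and 0.24 SD age-mix figures on assumed shares and effects. They show only that a bias comparable to the detectable difference is plausible.

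This concerns the secondary aim and the handling of items by mode, and does not invalidate the study. It should still be changed, because a better comparison can be made from information the protocol already plans to hold.

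**What to change.** In IV.E.2.b, for the general population sample:

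1. Report respondent composition by mode.
2. Estimate mode differences adjusted for, or weighted on, age stratum, geography stratum, race/ethnicity, socioeconomic status and medical history. Geography is in the sampling frame (IV.B.1); the rest are collected under IV.D.2. Education is not named there, so the plan should not depend on it. Medical history is itself reported in the mode used, so show results with and without it.
3. State that CASI-assigned women who answer on paper are analysed both as assigned and as completed.
4. Base any score calibration only on the adjusted difference. Check it against the estimate and confidence interval from clinical-sample women actually randomised to mode, excluding those placed in PAPI for lack of email. Agreement in direction alone is too weak a check. With at most 177 per mode in the non-postpartum clinical group, the SE is at least √(2/177) = 0.106 SD, so the interval will be wide (about ±0.21 SD or more).
5. Interpret Aim 4 response rates as those of each mode with its own contact schedule.

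The cost is a somewhat more complex comparison and a narrower response-rate claim, with no new data collection. Selection on unmeasured factors would remain and should be stated as a limitation.

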Validation of Bladder Health Instrument for Evaluation in Women (VIEW**)**

A Protocol for the Prevention of Lower Urinary Tract Symptoms (PLUS) Consortium

Protocol Committee:

[name], University of Minnesota
[name], University of California San Diego
[name], University of Minnesota
[name], University of Alabama at Birmingham
[name], Loyola
[name], Washington University
[name], University of Pennsylvania
[name], Yale
[name], University of Minnesota
[name], University of Michigan

Study Title	Validation of Bladder Health Instrument for Evaluation in Women (VIEW)
Study Design	Prospective observational
Primary Objective	To assess the reliability and validity of a Bladder Health Instrument (BHI) for measurement of bladder health among women across the life-course
Secondary Objective(s)	To evaluate effects of mode of administration of the BHI across paper and pencil versus electronic
Research Intervention(s)/Investigational Agents	N/A
IND/IDE # (if applicable)	N/A
Investigational Drug Services # (if applicable)	N/A
Study Population	Adult English fluent women
Sample Size (number of completes)	Total: n=1202 General population sample: n=694 Clinical evaluation sample: Asymptomatic & symptomatic: n=354 Post-partum sample: n=154
Study Duration for Individual Participants	General population: < 2 hour for BHI and survey completion (electronic or written) with up to six weeks for a subset of participants who complete both the initial validation questionnaire and those who also complete the re-test questionnaire for the reliability evaluation and 2 days documentation of symptoms on voiding diary. Clinical sample: Up to 8 weeks for completion of BHI (< 2 hr total) in addition to 3 days documentation of voiding (2 days symptoms + 1 day volume frequency) diaries prior to in-person visit, plus < 3 hour in-person visit including paper towel testing, uroflowmetry, post void residual and judge evaluation.

REVISION HISTORY

Version #	Date	Summary of changes from prior version	Consent Change?
Version 0.2	6/21/2018	Clarification of clinical evaluation tests Further revisions per team input Revised Table 1	
Version 0.3.1	7/5/2018	Addition of Figures 1, 4 and 5, revision of Figure 6. Creation of a Measures section. Further explanatory text in Analysis section.	
Version 0.4.1	9/24/2018	Addition Logistics survey administration, Re-formatting.	

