- **Aim 2. To develop and establish internal and external validity of a bladder health instrument (BHI) for use in clinical research.**
- **Aim 3. To develop and establish internal and external validity of a bladder health instrument (BHI) for use in a post-partum population.**

Measuring bladder health is central to all future work of the PLUS Research Consortium. As such, a main goal is to create and validate a BHI that is focused on assessing degrees of bladder health among an ethnically and geographically diverse population of community-dwelling women. In part, content validity for the BHI is currently being established based on expert opinion, adaptation of condition specific instruments, incorporation of language from prior PLUS studies involving focus groups and cognitive evaluation. The proposed research will extend this internal validation of the BHI by evaluating dimensional validity of the BHI. A further goal is to establish an external validation with a level of evidence that will allow valid inference to be made based on BHI score in both population based and clinical based research of community-dwelling women and post-partum women. The finalized instrument will be the end product of this study with internal validity (content, construct and dimensional), and external validity (criterion) established for the BHI.

Secondary Aim:

Aim 4. To evaluate the effect of mode of administration (paper and pencil vs. web-based) on item distributions, response rates, and validity.

The BHI is designed to be a self-administered questionnaire (SAQ). At the current time, paper and pencil (PAPI) and web-based/computer assisted self-administered (CASI) instruments are the primary modes the consortium is focusing on for validation of the BHI. There is an accumulation of evidence and knowledge of context based effects associated with mode of survey administration and the design of surveys for mixed-modes.⁴⁻⁷ With rapidly changing technology and increasing availability of online survey administration, the ability to optimally capture data is paramount. While some may prefer the PAPI administration, it is the

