future research using a validated BHI due to the known high risk of developing LUTS in the peripartum period and evidence for successful LUTS prevention strategies. Recalling peripartum LUTS is not accurate when done at a time remote from the delivery and is problematic in that the potential for recall bias is very high, resulting in significant measurement error.¹⁹ Adequate representation of this important population is critical to establish confidence that the BHI score will allow valid inference to be made by future studies of this population. Therefore, the sampling for the validation study includes a focal group of women who are in the postpartum period, defined for this study as 6-12 weeks post-partum, during the time of survey completion. Recruitment from the obstetric population (pregnant/post-partum) may occur simultaneously with those recruited from community and specialty clinics. The six research centers with access to these women will enroll participants. Due to the limited age range and limited range of bladder health in this population, we will use a convenience sampling technique without specific targets for distribution across LUTS. Broad demographic and racial representation will be emphasized and tracked.

IV.C.2 Recruitment and enrollment –Clinical evaluation sample

IV.C.2.a Community population

Prospective methods will be used for recruitment and data collection. Potential participants will be identified through local clinical research center practices, recruitment flyers and community engagement activities. The PLUS research centers may also partner with a family practice clinic, an OB clinic, or community centers. Enrollment will be targeted initially to healthy women (e.g., scheduling an appointment for an annual well-being visit or attending a local health fair). Other recruitment strategies may be proposed and individualized by site to maximally cover the spectrum of bladder health desired for this study. The distribution of LUTS within enrolled participants will be monitored by the SDCC and recruitment adjusted as necessary to ensure minimum representation of each symptom in the final clinical sample. Recruitment from local site specialty clinics may be necessary to fulfill the LUTS categories and will require a partial waiver of consent for pre-screening purposes to identify potential study participants with specific LUTS symptoms/severity.

Possible VIEW Recruitment Strategies:

Community and Asymptomatic Participants:

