Where practically possible, the participant-judge interaction will be scheduled to and actually occur prior to the administration of clinical tests. This is needed to minimize potential for test effects to influence participants interaction with the judge. Further, if the tests are performed before the clinical interview, the results may not be provided to the judge until after they have completed the interview and done the initial 1st and 2nd ratings.

Participants recruited from community or from non LUTS practices who report bothersome symptoms and request evaluation and treatment will be referred for clinical care per the individual PLUS research site's practices. For women recruited from LUTS medical practice/clinic, who were already scheduled for a new patient visit, any additional testing and evaluation beyond the clinical tests outlined above may be performed on the same day as the research appointment and will proceed per the provider's usual clinical practice. Information

gained from routine clinical care may be used in conjunction with clinical data collected for research purposes to inform the expert evaluator's 3rd and 4th rating of bladder health.

IV.E. Analyses

All analyses will be conducted on the general population and the clinical evaluation sample separately, data from the different sources will not be pooled. The final factor structure of the BHI scale will be determined based on the general population data. While the clinical evaluation sample data will not be pooled with the general population data, the clinical evaluation sample data provides a cost-effective means of conducting some external validity tests, i.e., it is not feasible to collect data for frequency/volume diaries or clinical evaluation measures or expert evaluator ratings for the general population sample.

IV.E.1. Distribution evaluation

IV.E.1.a. Ceiling and floor effects

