Sample sizes are based on several criteria. The basic rule of thumb for psychometric analysis (primarily correlation analyses) is 10 participants per survey item²⁹ although less conservative estimates of 5-10 participants per item³⁰ have been suggest. The BHI contains 2 general categories of question items: those asked of all respondents (global), and those that respondents will be branched into based on response to earlier screening type questions (LUTS-specific). The minimum number of global items under consideration for inclusion the BHI that a respondents could be asked is 53, with an additional 14 items a respondent could be branched into. Therefore the maximum number of global items that will be evaluated for inclusion in the BHI is 67. The number of global items is expected to be substantially reduced through the cognitive evaluation process. The minimum number of LUTS specific items under consideration for inclusion the BHI that a respondent could be asked is 6 (no experience of any LUTS), with up to an additional 12 items a respondent could be branched into, dependent on the number of LUTS experienced. Note it is unlikely that all of the symptom specific items will be applicable to or answerable by all respondents. Therefore, the maximum number of LUTS specific items that could be evaluated for inclusion in the BHI is 18. With a total maximum of all items included for evaluation for inclusion in the BHI being 85, the proposed sample size in aggregate, of n=1202 is sufficient under the most stringent or conservative criterion. Conducting factor analysis on each of the general population sample (n=694) and the clinical evaluation sample (n=508), still provides over 8 and 6 participants per item evaluated, respectively. This estimate is also conservative in that it assumes respondents will have experienced all 6 LUTS and therefore will be branched into the additional 12 LUTS items.

The sampled number of completes will be as follow:

Sample Completes	PAPI	CASI	Total
General Population	333	361	694
Retest	≥75	≥75	200
Clinical			
General	177	177	354
Post Partum			154
Total			1202

IV.F. Informed Consent

IV.F.1 General Population Surveys and Diaries

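### Aim 3 is a separate primary aim for postpartum women, but the analysis section names no analysis that isolates the 154 postpartum women from the 354 other clinical participants

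*Protocol*

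**What the plan says.** Protocol section II lists three primary aims. The third is "To develop and establish internal and external validity of a bladder health instrument (BHI) for use in a post-partum population". It stands beside Aim 2, which concerns clinical research.

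The synopsis gives the clinical sample in two parts, "Asymptomatic & symptomatic: n=354" and "Post-partum sample: n=154". Section IV.C.1.a and Table 1 fill the first part by quota across self-reported severity. Section IV.C.1.b takes the second part by convenience, giving as the reason "Due to the limited age range and limited range of bladder health in this population". IV.C.2.b confirms that no symptom cells are targeted there. IV.C.1.b also says that adequate representation of this group is critical to valid inference in later studies of it.

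Section IV.E opens with the rule "All analyses will be conducted on the general population and the clinical evaluation sample separately" and says that the final factor structure comes from the general population data. Section IV.E.3 justifies the sample size with "Conducting factor analysis on each of the general population sample (n=694) and the clinical evaluation sample (n=508", and sets these numbers against a maximum item count: "With a total maximum of all items included for evaluation for inclusion in the BHI being 85". Section IV.E.2.a.iii repeats the factor analysis by degree of LUTS. Section IV.E.2.c sets 0.20 as the minimum for the validity-diagonal correlations and adds three discriminant criteria.

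**The concern.** A primary aim about one population needs an estimate from that population. The only clinical set named in IV.E contains the postpartum women as a 30% minority, mixed with women sampled in a different way and over a wider range of bladder health. The planned partitions are by symptom level, mode and sample frame; none is by postpartum status.

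At stake is what may be concluded under Aim 3. A coefficient from the combined clinical set is driven mainly by the community women. It could meet the convergent criterion while the instrument tracks bladder health poorly in postpartum women. Section IV.A itself says that validation supports inference only in populations comparable to those used to validate. The exposure is chiefly in the external validity checks, because the scale structure is set elsewhere.

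**Working it through.** **Inputs from the protocol.** Community clinical women 354, postpartum women 154 (synopsis and the completes table in IV.E.3); clinical set 508, general population 694, maximum items 85, rule of thumb 10 per item or 5–10 per item (IV.E.3); convergent criterion 0.20 (IV.E.2.c). The protocol gives no expected correlations, means or SDs, so those below are assumptions.

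**1. The protocol's own figures.** 354 + 154 = 508, and 694 + 508 = 1202. Participants per item: 694/85 = 8.16 and 508/85 = 5.98, which match the stated figures of 8 and 6 to rounding (5.98 is just under the stated 'over 6'). The 508 is reached only by including the postpartum women. Without them the ratio is 354/85 = 4.16, below the lenient limit of 5.

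**2. Shares of the clinical set.** 354/508 = 69.7% community; 154/508 = 30.3% postpartum.

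**3. How far the larger group can carry a combined correlation.** Let r_c and r_p be the community and postpartum correlations and k the ratio of postpartum to community SD on both measures. With equal group means:

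r_combined = (354·r_c + 154·k²·r_p) / (354 + 154·k²)

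Set r_p = 0, the extreme case.

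- k = 1: the value reaches 0.20 when r_c = 0.20 × 508/354 = 0.287.
- k = 0.7: it reaches 0.20 when r_c = 0.20 × (354 + 154 × 0.49)/354 = 0.243.
- r_c = 0.30, k = 1: 354 × 0.30/508 = 0.209.
- r_c = 0.40, k = 0.6: 354 × 0.40/(354 + 154 × 0.36) = 0.346.

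**4. Where masking does not occur.** With r_c = 0.28 and k = 1, the value is 354 × 0.28/508 = 0.195, below the criterion. Mean differences also matter. Take r_c = 0.30, k = 1 and group means 0.5 SD apart. With weights 0.697 and 0.303, whose product is 0.211, the between-group term is 0.211 × 0.25 = 0.053.

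- Same direction on both measures: (0.209 + 0.053)/(1 + 0.053) = 0.25.
- Opposite directions: (0.209 − 0.053)/(1 + 0.053) = 0.15.

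**5. What 154 women can support alone.** Fisher z interval for an observed r = 0.20: atanh(0.20) = 0.203, SE = 1/√151 = 0.081, so the 95% CI is 0.04 to 0.35. For r = 0.30 it is 0.15 to 0.44. Items: 154/85 = 1.8 women per item, against 5 × 85 = 425 women under the lenient rule.

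**6. Effect of limited range on a postpartum correlation.** Assume the same slope and residual variance in both groups, r_c = 0.30, and a postpartum BHI SD of 0.6 of the community SD. Then r_p = 0.30 × 0.6/√(0.09 × 0.36 + 0.91) = 0.18/0.971 = 0.185. An instrument with an identical relation to the criterion would fall below 0.20 through restricted spread alone.

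**The case against.** The best counter-argument is that 508 appears only once, in a participants-per-item sentence about factor analysis, and never beside alpha or the criterion correlations. Elsewhere the protocol keeps postpartum women apart: their own line in the synopsis, their own row of completes, and their own recruitment group. IV.E says data from different sources are not pooled, and IV.E.2.a promises comparisons between and within sample frames. A SAP that is not shown could hold a postpartum table.

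Much of this stands. A reader might infer that the protocol fixes 508 as the set for every analysis; it does not say so. That extension rests on the two-set rule in IV.E, which covers all analyses. The no-pooling statement does not settle the matter, because IV.E and IV.E.2.c apply it to general population versus clinical evaluation, and IV.A names only those two recruitment populations. A separate row of completes sets a recruitment target, not an analysis. A SAP could add the split, but the protocol's analysis section should then agree with it.

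Three other points are fair. The general-population data already determine the scale structure, so the 508 factor analysis does not set the scale. The 0.20 is only the convergent criterion, and no text makes a combined 0.20 the test of Aim 3. Section I calls postpartum inclusion a secondary emphasis, although section II lists Aim 3 as primary.

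**Conclusion.** The point holds. Aim 3 is a primary aim, the analysis section names two sets, the clinical one is counted as 354 + 154, and no stated analysis isolates the 154. Followed as written, the plan does not answer Aim 3.

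The size of the masking risk depends on assumptions. With equal means and SDs and zero postpartum correlation, a community correlation of about 0.29 meets the criterion for the combined set; with a postpartum SD of 0.7 of the community SD, about 0.24 does. A reader might infer that the combined figure would always clear 0.20 whatever happens in postpartum women. The documents do not support that: a community value of 0.28 with equal SDs fails, and opposite mean shifts of 0.5 SD bring 0.30 down to about 0.15.

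A reader might also treat the missing clinical retest as part of this problem. It is separate. The revision history records its deliberate removal from the clinical sample, and this affects the 354 as much as the 154. What remains is a small wording mismatch: the between-frame comparison in IV.E.2.a covers test-retest, which is collected only in the general population.

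**What to change.** In IV.E, state that for Aims 2 and 3 internal consistency and the MTMM and criterion correlations are reported separately for the 354 community women and the 154 postpartum women. Each estimate should carry a 95% confidence interval and use the factor structure derived from the general population, as IV.E already specifies.

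Base Aim 3 conclusions on the postpartum estimates, not on the combined 508. Read them with their intervals and report the postpartum SD of the BHI and of each criterion beside the community SD. Do not apply a bare 0.20 cut: step 6 shows that limited range alone could fail an equally valid instrument, and step 5 shows how imprecise the estimate is.

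State that a separate postpartum factor analysis of the full item pool is not supported at 1.8 women per item. As a minor edit, exclude test-retest from the between-frame comparison in IV.E.2.a.

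The cost is protocol wording, matching SAP text, one more set of tables, and less precise estimates than the combined set would show. No new data are needed, since group membership is known at enrolment.
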